### 9.2.2 Outcome Measures: PrEP Comparison Component

#### 9.2.2.1 Primary Outcome Measures

[Table 5](#) summarizes the primary outcome measures for each study objective of the PrEP Comparison Component:

**Table 5: Primary Outcome Measures – PrEP Comparison Component**

Primary Outcome Measures – PrEP Comparison Component	
Objective	Outcome Measures
2.3.1	PrEP adherence: TDF-DP drug concentration level in Dried Blood Spots (DBS)
2.3.2	Maternal Adverse Events: 
 
Maternal Grade 3 or higher adverse events (signs, symptoms, labs, and diagnoses)
 
Maternal Grade 2 or higher chemistry abnormalities
 
 Adverse Pregnancy Outcomes: Composite outcome of 
 
Spontaneous abortion (occurring at <20 weeks gestation)
 
Stillbirth (occurring at ≥20 weeks gestation)
 
Preterm delivery (<37 completed weeks' gestation)
 
Small for gestational age (<10th percentile using INTERGROWTH-21st norms and ultrasound derived gestational age at delivery)
 
 Infant Safety: 
 
Infant death within the first 26 weeks of life
 
Infant Grade 3 or higher adverse events (signs, symptoms, labs, diagnoses) reported between birth and exit
 
Infant bone mineral content based on DXA scan of the whole body (WB-BMC) at birth and lumbar spine (LS-BMC) at birth and 26 weeks postpartum
 
Infant creatinine and CrCl rate at birth and 26 weeks postpartum
 
Infant length for age z-score at birth and exit
 

2.3.2	

### 9.2.2.2 Other Outcome Measures

Table 6 summarizes the other outcome measures for each study objective of the PrEP Comparison Component:

**Table 6: Other Outcome Measures – PrEP Comparison Component**

Other Measures – PrEP Comparison Component	
Objective	Outcome Measure
2.4.1	PrEP adherence: TDF-DP drug concentration level in DBS
2.4.2	Sexual risk behavior 
 
Any condomless vaginal or anal sex
 
Incident sexually transmitted infection defined as any new HSV, syphilis, chlamydia or gonorrhea infections during follow-up
 
Incident HIV infection
 

2.4.3	
 
Antiretroviral drug resistance: presence of virus resistant to TDF at time of HIV diagnosis
 

2.4.4	Bone mineral density – Mean maternal bone mineral density (g/m  ) based on DXA scan of the lumbar spine (LS-BMD) and hip (H-BMD) at delivery and 26 weeks postpartum

### 9.2.2.3 Exploratory Outcome Measures

**Table 7** summarizes the exploratory outcome measures for each study objective of the PrEP Comparison Component:

**Table 7: Exploratory Outcome Measures – PrEP Comparison Component**

Exploratory Outcome Measures – PrEP Comparison Component	
Objective	Outcome Measures
2.5.1	Microbiome – PrEP or no PrEP exposure 

• Compare the maternal vaginal/rectal microbiome, differences in diversity (continuous), bacterial composition (continuous) and relationship to blood and cervicovaginal drug levels (continuous) longitudinally at study entry, late pregnancy, six weeks post-partum and 26 weeks post-partum

• Compare the infant microbiome differences in diversity and bacterial composition initially at six weeks post-partum and 26 weeks post-partum

### 9.2.3 Randomization and Stratification

There will be no randomization for this study. To monitor the balance of the maternal participants enrolled among various groups, the enrollment will be stratified by:

- Cohort: PrEP vs. No PrEP at enrollment
- Trimester of enrollment during pregnancy: 2nd trimester vs. 3rd trimester
- Country
- Age at enrollment: 16-17 years vs. 18 years of age and older

Stratifying by the above factors in this non-randomized study is for the purpose of monitoring the accrual to ensure that there are not large differences between the two cohorts (PrEP and No PrEP) in the proportion of women who are 16-17 years old, who are from a specific country, or who enroll in the 2nd (vs. 3rd) trimester of pregnancy, and to ensure a proportion of enrolled women are in the 16-17 year old age group.

### 9.2.4 Sample Size and Accrual

The PrEP Comparison Component will enroll a total of 350 (233 in Cohort 1 and 117 in Cohort 2) women over a 12-month period. Women will be followed through 26 weeks postpartum. Expected duration of follow-up for a given maternal participant is between 7 and 12 months depending on the gestational age of the pregnancy at enrollment. The following sample size and power calculations assume a final analysis sample of 300 women (200 in Cohort 1 and 100 in Cohort 2). The primary reason for the 2:1 enrollment into the two cohorts was to balance the need for a “No PrEP” comparison group (to provide the background rates for safety outcome measures) with the need for a large enough PrEP group to examine outcomes that would be restricted to women in that group (Adherence). To achieve this sample size at the analysis phase, this study will enroll ~350 women to accommodate a decrease of ~15% due to maternal attrition.

**Table 8** shows the expected precision of a range of PrEP adherence estimates across different sample sizes in Cohort 1. For example, with a sample size of 200 women in Cohort 1, the width of the 95% confidence interval for an estimated adherence rate of 75% is 13%.

**Table 8: Precision (shown as 2-sided 95% confidence intervals) of different estimates of the proportion with good adherence (for illustration, defined as meeting or exceeding the threshold corresponding to protective drug levels of TFV-DP) at different sample sizes for Cohort 1.**

% Adherent	Sample Size in Cohort 1			
	150	200	250	300
50	42-58%	43-57%	44-56%	44-56%
60	52-68%	53-67%	54-66%	54-66%
65	57-73%	58-72%	59-71%	59-70%
70	62-77%	63-76%	64-76%	65-75%
75	67-82%	68-81%	69-80%	70-80%
80	73-82%	74-85%	75-85%	75-84%

**Table 9** below shows the precision of estimates of safety outcomes (e.g. preterm birth) expected with a range of event rates and a sample size of 200 women in Cohort 1 and 100 women in Cohort 2. It is expected that the rates of these outcomes will be low particularly since this is a young group of healthy HIV uninfected women. To that end, a range of AE rates with corresponding confidence intervals is included in the protocol.

**Table 9: 95% Confidence Intervals for different possible event rates of safety outcomes in Cohort 1 (n=200) and Cohort 2 (n=100)**

Event Rate	95% Confidence Interval	95% Confidence Interval
	Cohort 1 (n=200)	Cohort 2 (n=100)
0.5%	(0, 2.8)	(0, 3.6)
2.0%	(0.5, 5.0)	(0.2, 7.0)
4.0%	(1.7, 7.7)	(1.1, 9.9)
10.0%	(6.2, 15.0)	(4.9, 17.6)
15.0%	(10.4, 20.7)	(8.6, 23.5)
20.0%	(14.7, 26.2)	(12.7, 29.2)
30.0%	(23.7, 36.9)	(21.2, 40.0)

The study allows adequate power to detect moderate cohort differences from 8.5% to 16%, depending on the true background rate of the event, as summarized below in **Table 10**. The table shows minimum detectable differences in safety outcomes between Cohort 1 and Cohort 2 which could be achieved with 80% power and alpha=0.05. For example, based on a sample size of 200 in Cohort 1, and assuming a 2:1 enrollment among women agreeing to and declining PrEP, differences of at least 13% will be detectable between the two cohorts in the proportion of maternal adverse events for events with a 10% background rate (10% in Cohort 2, 23% in Cohort 1).

**Table 10: Minimum detectable differences in safety outcomes based on evaluable sample size of 300 for Cohort 1(n=200) and Cohort 2 (n=100), 80% power, alpha=0.05**

% with event in Cohort 2 (N=100)	% with event in Cohort 1 (N=200)	Odds Ratio
2%	10.5%	5.8
5%	15.6%	3.5
10%	23%	2.67
15%	29%	2.36
20%	35%	2.19
25%	41%	2.10

To address primary objective 2.3.2, the mean bone mineral content of infants at birth and at age 26 weeks will be estimated and differences in mean bone mineral content between infants in Cohort 1 and Cohort 2 will be evaluated using two sample t tests. **Table 11** shows the statistical

power the study would have to detect a range of estimated differences in means. For example, with a sample size of 200 in Cohort 1 and 100 in Cohort 2 this study will be able to detect differences in mean bone mineral content of at least 0.35 SD with 80% power. Based on the SMARTT study in the U.S., assuming a standard deviation of 16.6 (77) this would be equivalent to a difference in means of 5.81g. Assuming a standard deviation of 14.9 found in the P1084s study (79) this would be equivalent to a difference in means of 5.22 g.

**Table 11: Estimated Power to Detect the Mean Differences in Infant Growth Outcomes Infant DXA, Whole Body Bone Mineral Content (BMC) (g) at Birth (Mean=63.8, SD=16.6)\*\***

Difference to be Detected	Effect Size (SD)	Power (based on sample sizes*)		
		N1=200 N2=100	N1=180 N2=90	N1=160 N2=80
4% (of 63.8)	2.55 (16.6)	24%	22%	20%
5%	3.19	35%	32%	29%
6%	3.83	47%	43%	39%
7%	4.47	59%	55%	50%
8%	5.10	71%	66%	61%
9%	5.74	80%	76%	71%
10%	6.38	88%	84%	80%
0.25*SD	4.15	53%	49%	44%
0.30*SD	4.98	68%	64%	59%
0.35*SD	5.81	81%	77%	72%
0.40*SD	6.64	90%	87%	83%
0.45*SD	7.47	96%	94%	91%
0.50*SD	8.30	98%	97%	95%
0.75*SD	12.45	> 99%	> 99%	> 99%

\*Sample Sizes: N1 -- Cohort 1 (PrEP), N2 – Cohort 2 (no PrEP)

\*\*Data were from PHACS SMARTT Study (Siberry, 2015)

To address other objective 2.4.4, the mean bone mineral density of the lumbar spine and of the hip of women at delivery and at 26 weeks post-delivery will be estimated and differences in mean bone mineral density between women in Cohort 1 and Cohort 2 will be evaluated using two sample t tests. Table 12 shows estimated statistical power to detect a range in differences in mean maternal bone mineral density that the study could detect given different sample sizes. For example, with a sample size of 300 (200 PrEP and 100 no PrEP) the study would have at least 80% power to detect a minimum 4% difference in mean BMD and .35 SD difference in means between groups at delivery and 26 weeks postpartum.

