Incidence rate ratio (among PrEP exposed vs. PrEP unexposed women) of cumulative adverse events up to 26 weeks postpartum	Incidence rate ratio of cumulative AEs up to the week-26 postpartum visit (among PrEP exposed vs. PrEP unexposed women) estimated based on Poisson distribution (with 95% Wald CI).

Supplemental Analyses:

- Analyses will be repeated stratified by time period (i.e., antepartum (AP) and postpartum (PP), and within AP stratified by gestational age category of enrollment).
- Rates of maternal adverse events in AP and PP periods will also be calculated and compared across levels of PrEP adherence (based on TFV-DP levels in dried blood spots). Models will be fit adjusting for potential confounders.

- To compare time to first adverse event in PrEP exposed vs. PrEP unexposed women, the hazard ratio (95% CI) will be estimated with Logrank test p-value from Cox proportional hazards regression on time to first AE with PrEP exposure as a time-varying covariate.

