
 • Incidence rate ratio (among PrEP exposed vs. PrEP unexposed infants) of cumulative adverse events up to the age 26-week visit 	
 • Incidence rate ratio of cumulative adverse events up to the age 26-week visit (among PrEP exposed vs. PrEP unexposed infants) estimated based on Poisson distribution (with 95% Wald CI).

Supplemental Analyses:

- Analyses will be repeated stratifying by time of infant drug exposure (i.e., antepartum (AP) and postpartum (PP), and within AP stratified by gestational age category of maternal enrollment).
- Rates of infant adverse events will also be calculated and compared across levels of maternal PrEP adherence (based on TFV-DP levels in dried blood spots). Models will be fit adjusting for potential confounders.
- To compare time to first infant adverse event in PrEP exposed vs. PrEP unexposed infants, the hazard ratio (95% CI) will be estimated with Logrank test p-value from Cox proportional hazards regression on time to first AE with PrEP exposure as a time-varying covariate.

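### At the 2% row of Table 10, the planned Poisson rate ratio with a Wald interval falls short of the stated 80% power and gives no interval when the comparator has no events

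*Protocol*

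**What the plan says.** Protocol 9.2.4 sizes the PrEP Comparison Component on completers: "power calculations assume a final analysis sample of 300 women (200 in Cohort 1 and 100 in Cohort 2"). Enrolment is larger; the component "will enroll a total of 350 (233 in Cohort 1 and 117 in Cohort 2"), "to accommodate a decrease of ~15% due to maternal attrition".

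Table 10 then lists minimum detectable differences in safety outcomes "which could be achieved with 80% power and alpha=0.05". It gives the percentage with an event in each cohort and an odds ratio. Its first row is 2% in Cohort 2 against 10.5% in Cohort 1, odds ratio 5.8. The summary above the table reads "The study allows adequate power to detect moderate cohort differences from 8.5% to 16" per cent. The 8.5 is that first row. No test is named. The same section says "It is expected that the rates of these outcomes will be low".

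Protocol 9.2.6 planned Cox regression for adverse events. The SAP makes Cox supplemental. Its primary summary for maternal events (6.3.2) is an incidence rate ratio "estimated based on Poisson distribution (with 95% Wald CI"), and for infants (6.3.4) the same ratio ("among PrEP exposed vs. PrEP unexposed infants) estimated based on Poisson distribution (with 95% Wald CI")). SAP 2.4.2 repeats the sample size, refers back to the protocol and gives no power for a rate ratio. Neither document says what is reported if one group has no events.

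**The concern.** The stated power belongs to a comparison of two proportions, while the primary adverse-event analysis is a log rate ratio with a Wald interval. The two behave alike when events are plentiful. They diverge when the smaller group has only a handful, because the standard error of the log rate ratio is driven by the reciprocal of the smaller count. With 2% background risk and 100 comparator women the expected count is 2. At a count of 1 the standard error is already above 1, and at 0 it is infinite.

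Objective 2.3.2 is a primary safety objective, and infant death within 26 weeks is among its outcomes. At this row a five-fold excess (10.5/2 = 5.25) would be missed by the planned interval in roughly 36-42% of trials with 100/200, against the 20% that Table 10 implies. The interval is also missing exactly when every event falls on the PrEP side.

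**Working it through.** **Inputs.** Table 10, first row: p0 = 0.02, p1 = 0.105, n0 = 100, n1 = 200, 80% power, alpha 0.05 (two-sided assumed; it reproduces the table). Enrolled numbers 117 and 233 (protocol 9.2.4). Analysis method from SAP 6.3.2 and 6.3.4.

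**1. Reproduce Table 10.** Pooled two-proportion test without continuity correction:

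power = Φ{ [|p1 − p0| − 1.96·SE0] / SE1 }

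- Pooled p = (2 + 21)/300 = 0.0767
- SE0 = √[0.0767 × 0.9233 × (1/100 + 1/200)] = 0.0326
- SE1 = √[0.02 × 0.98/100 + 0.105 × 0.895/200] = 0.0258
- (0.085 − 1.96 × 0.0326)/0.0258 = 0.82, so power = 79.4%

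All six rows on the printed percentages: 79.4, 79.6, 80.6, 78.0, 77.8, 79.1%. On the percentages implied by the printed odds ratios: 79.3-80.1%. The table is internally sound as a two-proportion calculation.

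**2. Planned analysis at the same row.** With event counts x0 and x1, the Wald interval excludes 1 when

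|ln[(x1/n1)/(x0/n0)]| > 1.96 × √(1/x0 + 1/x1)

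For 100/200 this needs at least 16 Cohort 1 events if x0 = 1, 18 if x0 = 2, 21 if x0 = 3 and 24 if x0 = 4. With x0 = 0 no finite interval exists, so that case counts as no rejection. The expected Cohort 1 count is 200 × 0.105 = 21. Summing over all (x0, x1):

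| How events are counted | Wald power, 100/200 | Wald power, 117/233, no loss |
|---|---|---|
| Poisson, mean n·p | 57.6% | 72.1% |
| Each woman once, full person-time (binomial) | 58.6% | 73.1% |
| Poisson, mean −n·ln(1 − p) | 63.3% | 76.7% |
| First event, time stopped at event | 64.4% (simulated) | 76.8% (expected person-time) |

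Between the two columns: if the 15% who leave are lost halfway on average (an assumption), 7.5% of person-time goes, leaving about 108/216, and the first three models give 65-70%. Step changes pull the other way on comparator time. Moving 10% of Cohort 2 person-time to the exposed side at 100/200 gives 51-57%, and 20% gives 37-44%. The documents give no step-change rate, so these are illustrations only.

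**3. No comparator events.** 0.98^100 = 13.3%; 0.98^117 = 9.4%.

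**4. Rate needed for 80% with the Wald interval.** At a 2% background and 100/200, Cohort 1 would need about 13% (mean −n·ln(1 − p)) to 14% (mean n·p).

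**5. Higher rows, 100/200, Wald.**

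| Background | Once per woman, full time | First event, time stopped (simulated) | Counts at −n·ln(1 − p) |
|---|---|---|---|
| 5% | 74.0% | 78.6% | 80.5% |
| 10% | 73.6% | 80.4% | 83.7% |
| 15% | 67.4% | 77.1% | 82.5% |
| 20% | 64.2% | 77.2% | 83.5% |
| 25% | 61.8% | 78.0% | 86.0% |

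The SAP variable is the occurrence of at least one event, but the summary is a rate of cumulative events, so the documents do not settle which column applies.

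**6. Alternatives at the 2% row, 100/200.** Same enumeration; type I error at 2% versus 2%.

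| Method | Power | Type I error |
|---|---|---|
| Score | 79.3-83.1% | 3.9-4.1% |
| Exact mid-P (conditional) | 81.8-85.5% | 2.7-2.8% |
| Profile likelihood | 84.4-87.5% | 8.2-8.4% |

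Both score and mid-P remain defined at x0 = 0. With 0 versus 8 events the two-sided mid-P value is 2 × 0.5 × (2/3)^8 = 0.039, and the score statistic is (8 − 5.33)/√(8 × 2/3 × 1/3) = 2.0.

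**The case against.** Several counter-arguments have force.

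- **The log-rank test.** Under both estimands the SAP lists a supplemental Cox model for time to first event with a log-rank p-value. Log-rank is a score-type test, stays defined with zero events in one group, and would have close to the stated power here. This stands, and a split such as 21 versus 0 would be visible in the report. But it is supplemental and supplies a p-value; it does not supply the primary interval.
- **Power is already described as limited.** Protocol 9.2.1 says so for safety conclusions, and calls the intervals descriptive. This softens the consequence. It does not correct the specific 80% in Table 10, and that section speaks of large differences where 9.2.4 speaks of moderate ones.
- **The analysis set is everyone enrolled.** SAP 6.3.2 uses all enrolled women, so 58-64% is a completers' figure. Accepted: 72-77% with no loss is the matching upper case, and it is still below 80%.
- **The 2% rate is not tied to an endpoint.** No section assigns 2% to a primary adverse-event outcome, and the protocol's worked example uses 10%. Accepted; but the 2% row supplies the 8.5 in the headline claim, and low rates are expected.
- **The test behind Table 10 is inferred.** True. At the 2% row Fisher's exact test (80.6%) fits as well. Either is a two-proportion test.
- **The detail may sit in the Analysis Implementation Plan**, to which the SAP defers and which is not available here. A zero-event rule may be there.

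A reader might infer that all of Table 10 is overstated. The documents do not support that: from 5% upward, power runs from 62% to 86% depending on counting. A reader might also infer that the adverse pregnancy outcome is affected; SAP 6.3.3 analyses it by odds ratio, so this mismatch does not arise. Nor do the documents show that a null result would be presented as reassurance.

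**Conclusion.** The point holds at the sparse end of Table 10. For 2% versus 10.5%, the planned Wald rate-ratio analysis has about 58-64% power with 100/200 and 72-77% with 117/233 and no lost person-time, against a stated 80%. It has no finite interval in about 13% or 9% of trials respectively. The figures assume two-sided alpha 0.05, a zero comparator count treated as not significant, and no step changes. They carry over to infants only so far as the infant groups are of similar size.

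The zero-event gap is a defect in its own right, whatever view is taken of power. The remedy costs almost nothing, so it is worth making the change before the analysis.

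**What to change.** 1. **SAP 6.3.2 and 6.3.4:** replace the Wald interval with an exact mid-P conditional or a score 95% interval for the Poisson rate ratio. Either stays defined with zero events in one group. At the 2% row with 100/200 they give 79-86% power with type I error of 4.1% or less. Do not substitute profile likelihood: at this sparsity its type I error is about 8%, so part of its apparent power is bought with alpha.
2. **Protocol 9.2.4:** state that Table 10 describes a two-proportion comparison. If the Wald interval is kept, restate the 2% row for the rate ratio: about 58-64% power with 100/200, and about 13-14% in Cohort 1 needed for 80%.

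The cost is one sentence in each of two SAP tables and a note or a recomputed row in the protocol. No data, visits or participants are added. The downside is an asymmetric interval that is slightly less familiar to readers, and one-sided when a group has no events.

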**Table 12: Estimated Power to Detect the Mean Differences in Maternal Growth Outcomes**  
**Maternal DXA, Whole Body Bone Mineral Content (BMC) (g)**  
**(Mean=0.979, SD=0.111)\*\***

BMD	Difference to be Detected	Effect Size (SD*)	Power (based on sample sizes**)		
			N1=200 N2=100	N1=180 N2=90	N1=160 N2=80
Lumbar Spine	1% (of 0.979*)	0.0098 (0.111*)	11%	10%	10%
	2%	0.0196	30%	28%	25%
	3%	0.0294	58%	53%	49%
	4%	0.0392	82%	78%	73%
	5%	0.0490	95%	93%	89%
	6%	0.0587	99%	98%	97%
	0.10*SD	0.0111	13%	12%	11%
	0.15*SD	0.0167	23%	21%	19%
	0.20*SD	0.0222	37%	34%	31%
	0.25*SD	0.0278	53%	49%	44%
	0.30*SD	0.0333	69%	64%	59%
	0.35*SD	0.0389	81%	77%	72%
	0.40*SD	0.0444	90%	87%	83%
Total Hip	1% (of 0.968*)	0.0097 (0.119*)	10%	10%	9%
	2%	0.0194	26%	24%	22%
	3%	0.0290	51%	47%	43%
	4%	0.0387	75%	71%	66%
	5%	0.0484	91%	88%	84%
	6%	0.0581	98%	97%	94%
	0.10*SD	0.0119	13%	12%	11%
	0.15*SD	0.0179	23%	21%	19%
	0.20*SD	0.0238	37%	34%	31%
	0.25*SD	0.0298	53%	49%	44%
	0.30*SD	0.0357	68%	64%	59%
	0.35*SD	0.0417	81%	77%	72%
	0.40*SD	0.0476	90%	87%	83%

\*Data were from JAIDS (Mirembe, 2015): mean (SD) = 0.979 (0.111) for lumbar spine; mean (SD) = 0.968 (0.119) for total hip.

\*\*Sample Sizes: N1 -- PrEP Arm, N2 -- non-PrEP Arm

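### Section 9.2.4 states at least 80% power for a 4% difference in maternal BMD without naming a site, but at the total hip the design gives 75%; one cell of Table 8 is also wrong

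*Protocol*

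**What the plan says.** For other objective 2.4.4, Protocol section 9.2.4 says that "the mean bone mineral density of the lumbar spine and of the hip of women at delivery and at 26 weeks post-delivery will be estimated". It adds that "differences in mean bone mineral density between women in Cohort 1 and Cohort 2 will be evaluated using two sample t tests". The next sentences refer to Table 12 and give an example: with 200 women on PrEP and 100 not on PrEP, "the study would have at least 80% power to detect a minimum 4% difference in mean BMD", and likewise a difference of 0.35 SD, at delivery and at 26 weeks postpartum. The example names no site.

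Table 12 has separate blocks for the two sites. Its footnote gives a mean (SD) of 0.979 (0.111) for the lumbar spine and "mean (SD) = 0.968 (0.119) for total hip". For a 4% difference it prints:

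| Site | 200/100 | 180/90 | 160/80 |
|---|---|---|---|
| Lumbar spine | 82% | 78% | 73% |
| Total hip | 75% | 71% | 66% |

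For 0.35 SD with 200/100 it prints 81% at both sites.

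In the same section, Table 8 gives 95% confidence intervals for the proportion adherent in Cohort 1. For 80% adherent it prints 73-82% with 150 women and 74-85% with 200.

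**The concern.** The paragraph sets up two BMD endpoints and then makes one unqualified power statement. Table 12 contradicts that statement for the hip. The sentence also pairs 4% with 0.35 SD. The two are nearly the same difference at the spine but not at the hip, where the SD is larger relative to the mean.

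This is the only power claim for maternal BMD made in prose, so it is the one likely to be carried into the later analysis plan or a report. Protocol section 1.5 states a BMD hypothesis for both sites, and Table 6 lists hip BMD as an outcome. A reader who relies on the sentence would credit the hip comparison with more power than it has.

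The Table 8 cell fails on its face. The interval is 9 points wide with 150 women and 11 points wide with 200, so precision would appear to worsen as the sample grows. It also reaches 7 points below 80% but only 2 above. Table 8 describes precision for the adherence proportion, which is a primary outcome.

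**Working it through.** **Inputs**
- Group sizes 200 and 100, means and SDs: Protocol section 9.2.4 and the Table 12 footnote. The 300 is the analysis sample after attrition; section 9.2.4 says that "this study will enroll ~350 women to accommodate a decrease of ~15% due to maternal attrition".
- Test: two-sample t-test (section 9.2.4).
- Alpha: stated as 0.05 for Table 10 only. Two-sided 0.05 is assumed for Table 12, and the assumption is supported because it reproduces that table.

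**Formula.** The standardised difference is d = (0.04 × mean) / SD. The noncentrality is d / √(1/200 + 1/100) = d / √0.015 = d / 0.1225. Power comes from the noncentral t with 298 degrees of freedom (critical value 1.968). The normal approximation is Φ(noncentrality − 1.960).

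**Lumbar spine, 4%**
- Difference 0.04 × 0.979 = 0.0392; d = 0.0392 / 0.111 = 0.353; noncentrality 2.88.
- Power 81.9% (noncentral t) or 82.1% (normal). Table 12 prints 82%, so both the table and the 80% statement reproduce.

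**Total hip, 4%**
- Difference 0.04 × 0.968 = 0.0387; d = 0.0387 / 0.119 = 0.325; noncentrality 2.66.
- Power 75.4% (noncentral t) or 75.7% (normal). Table 12 prints 75%, so the table reproduces, but the sentence's 80% does not. The gap is 80 − 75.4 = 4.6 points.
- With 180/90 and 160/80, power is 70.9% and 65.8%. Table 12 prints 71% and 66%.

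**Difference detectable with 80% power, 200/100.** This is 0.344 SD at either site.
- Spine: 0.344 × 0.111 / 0.979 = 3.9%.
- Hip: 0.344 × 0.119 / 0.968 = 4.2%.

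**The 0.35 SD in the same sentence.** Power is 81.3% at either site, so this part is right. As a percentage of the mean:
- Spine: 0.35 × 0.111 / 0.979 = 4.0%.
- Hip: 0.35 × 0.119 / 0.968 = 4.3%.

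**Could another assumption rescue 80% at the hip?**
- One-sided alpha 0.05 gives 84% at the hip, but it also gives 89% at the spine, where Table 12 prints 82%. The protocol did not use it.
- The enrolled numbers, 233/117, give 81.7%, and an equal split of 150/150 gives 80.2%. The sentence fixes 200/100.
- With 2:1 allocation, 80% power for 4% at the hip would need about 224/112 evaluable women.

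**Table 8, 80% adherent, n = 150.** The observed count is 0.80 × 150 = 120. The Clopper-Pearson interval for 120/150 is 72.7% to 86.1%, that is 73-86%. A simple normal interval is 80% ± 1.96 × √(0.8 × 0.2 / 150) = 80% ± 6.4 points, with an upper limit of 86.4%. The printed upper limit of 82% is about 4 points too low. The other 23 cells of Table 8 match the Clopper-Pearson limits to within rounding.

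**The case against.** The best defence is that the sentence was written about the spine. It is offered as an example, it never says that it covers both sites, the heading of Table 12 carries only the spine mean and SD, and 4% and 0.35 SD coincide at the spine. The authors may well have been reading the spine rows. This probably explains how the sentence arose. It does not make it correct, because the paragraph has just defined the comparison as spine and hip and the claim is left unrestricted.

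It is also true that nothing is hidden: the correct hip figure is printed in Table 12 directly below. Maternal BMD is not a primary outcome, and SAP section 1.1 leaves other objectives to a separate plan. The SAP's sample-size overview (section 2.4.2) does not repeat the 4% claim. Nothing in the documents says that a non-significant hip result will be read as excluding a 4% loss, so that harm is possible but speculative. All of this limits the importance of the point and none of it removes the contradiction.

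On Table 8, the planned size is 200, and that cell is correct. The value 82% is also the upper limit in the cell directly above, which suggests a copying slip. SAP section 6.3.1 specifies Clopper-Pearson limits calculated from the data, so the misprint cannot affect the reported interval.

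**Conclusion.** Wrong as written. With 200 and 100 women and two-sided alpha 0.05, power for a 4% difference in mean BMD is about 82% at the lumbar spine and about 75% at the total hip, so the unqualified statement of at least 80% fails at the hip by about 5 points. The 0.35 SD statement is correct at both sites, and the Table 12 entries at 4% and at 0.35 SD are correct; the fault lies in the summary sentence. The conclusion rests on the means and SDs in the Table 12 footnote, on the two-sided alpha that reproduces the table, and on reading the sentence as covering the two sites that its paragraph introduces. The Table 8 cell for 80% adherent with 150 women is a separate, smaller error of about 4 points in the upper limit. Both should be corrected, but neither bears on sample size, design or the planned analyses.

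**What to change.** In Protocol section 9.2.4, restate the example along these lines: *with 200 and 100 women there is at least 80% power for a 4% difference at the lumbar spine and a 4.3% difference (0.35 SD) at the total hip; power for 4% at the hip is 75%.* The 4.3% keeps the existing 0.35 SD, at 81% power; the exact 80% point at the hip is 4.2%. In Table 8, change the cell for 80% adherent and n = 150 to 73-86%. Carry the corrected power statement into the separate SAP for other objectives.

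The cost is one sentence and one table cell. The stated hip power becomes slightly less favourable, and nothing else changes.
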